### **8.3 Off-Agent Criteria**

Participants may stop taking study agent for the following reasons: completed the protocol-prescribed intervention, AE or serious adverse event (SAE), inadequate agent supply, noncompliance, concomitant medications, medical contraindication, or decision by the participant to proceed with surgery for DCIS. In this event, the participant will be asked to continue study medication until the day before surgery, as long as she has taken study medication for 4 weeks or more. Participants will continue to be followed, if possible, for safety reasons. Participants who stop agent within 6 days of surgery will continue their study visits to collect endpoint data according to the schedule of events, unless the participant withdraws consent for further study procedures.

### **8.4 Off-Study Criteria**

8.4.1 Participants may go “off-study” for the following reasons: completed the protocol-prescribed intervention, AE or serious adverse event, lost to follow-up, inadequate agent supply, noncompliance, concomitant medications, medical contraindication/pregnancy, withdraw consent, determination of ineligibility (including screen failure), death, or investigator’s discretion. Participants will continue to be followed, if possible, for safety reasons. Participants who stop agent within 6 days of surgery will continue their study visits to collect endpoint data according to the schedule of events, unless the participant withdraws consent for further study procedures.

8.4.2 For the primary analysis (intent to treat, ITT) any participant that received study agent and has tissue available will be included. A per protocol analysis will then be completed which removes noncompliant participants or participants who went off study prior to 4 weeks. For these analyses, participants who complete 4 weeks of study agent will be considered evaluable.

8.4.3 Pregnancy would be considered a medical contraindication to continued use of the study agents. If a pregnancy occurs, the patient will be followed through the resolution of the pregnancy and the outcome of the pregnancy will be recorded. Some pregnancy outcomes are considered to be an SAE (e.g. miscarriage, birth defect) and must be reported following the SAE procedures in section 11.

### **8.5 Study Termination**

NCI, DCP as the study sponsor has the right to discontinue the study at any time.

## **9. CORRELATIVE/SPECIAL STUDIES**

### **9.1 Rationale for Methodology Selection**

The primary endpoint is Ki67 labelling by IHC; this is a widely used and validated assay, and no other proliferative assay has reached the same level of methodological or biological validation. It was also the primary endpoint for our prior study (NWU 07-9-02) and will therefore be most appropriate for the present protocol. [name] (NU pathologist) will mark the DCIS legion of H&E slides to be evaluated by biomarker IHC assays.

Ki67 IHC staining and scoring will be performed at the Northwestern University Pathology Core Facility.

Secondary endpoints include the Oncotype DCIS Score, which will be performed by Exact Sciences and is also highly standardized and quality-controlled; No other methodology is available for measurement of this parameter.

Other IHC staining and scoring of COX-2, CD68, and p16 will be also performed at the Northwestern University Pathology Core Facility.

Tissue and plasma drug concentrations and hormone levels will be measured at the Hormone Laboratory of Haukeland University Hospital, Norway.

## 9.2 Comparable Methods

Our assays have been carefully selected with comparability in mind, and all are comparable to prior studies, our own as well as those of other investigators.

# 10. SPECIMEN MANAGEMENT

[figure not shown]
## 10.1 Laboratories

- Pathology Core Facility (PCF) of Northwestern University (specimen receiving, logging, tracking, distribution, sectioning of blocks, H&E staining and IHC marker staining and scoring).
- Exact Sciences (DCIS Score)
- Hormone Laboratory of Haukeland University Hospital, Norway (steroid hormone assays and drug concentration assays on tissue and blood)
- Northwestern University Comprehensive Metabolic Core Lab (IGF-1, IGFBP-3, and SHBG)
- Northwestern Memorial Hospital Hemostasis Lab (coagulation panel– Factor IX and von Willebrand Factor assays)
- Quest Diagnostics (coagulation panel – Factor VIII activity and total Protein S antigen assays)

## 10.2 Collection and Handling Procedures

### 10.2.1 Amount of sample

- Blood samples (Screen 1 and Study Visit 1): Blood samples will be collected with an appropriate type of anti-coagulants, and processed as described in session 7.1 (the schedule of event table footnote #5 and #11). 1) **Two** 2.7mL blue top tubes (citrate) to obtain plasma for coagulation panel assays. Each tube must be a full draw. 1mL each will be aliquoted in a 1.8 mL size cryo-vial. We will make as many aliquots as available. The last aliquot may not be enough for 1 mL, but save it as well and record approximate volume available. 2) **Two** 10 mL lavender top tubes (K2EDTA) to obtain plasma and buffy coat. We will get approximately 3~4 mL plasma from one lavender top tube. 1mL each will be aliquoted in a 1.8 mL size cryo-vial. We will make as many aliquots as available. The last aliquot may not be enough for 1 mL, but save it as well and record approximate volume available. Plasma aliquots will be used for IGF-1 and SHBG assays (Screen 1 and Study Visit 1); for steroid hormone assays (estradiol, progesterone, and dehydroepiandrosterone (DHEA), androstenedione, and testosterone (Screen 1 and Study Visit 1); and for measuring tamoxifen and its metabolites [tamoxifen, N-desmethyl tamoxifen, (E) 4-OHT, (Z) 4-OHT, (E) endoxifen, and (Z) endoxifen] (Only Study Visit 1). Finally, buffy coat will be collected into one 1.8 mL cryo-vial. A total volume of buffy coat will be approximately 1 mL for future polymorphisms assays in tamoxifen metabolism

genes (Screen 1 and Study Visit 1). Please refer lab manual for more details on sample handling, storage and shipping.

[figure not shown]
A minimum of 15 sections will be cut from the core needle biopsy block and the surgical block, 7 for Ki67 and other IHC markers and 8 for DCIS score measurement.

- Drug concentration assays (only for study visit 1): 1) Fresh benign tissue 1x1x1 cm fragments (weight of each fragment is usually 200mg~300mg) from locations defined in **Figure 2**, from surgical cavity, to avoid interfering with margin assessment on the main specimen. The 1x1x1 cm breast tissue sample will be split in half, and a slice of tissue about 3 mm thick, (see Figure 2A, bottom right panel, piece B in red) will be taken from one face, and placed in formalin for at least 6 and at most 72 hours, then embedded in paraffin. The remainder (piece A in yellow) of the fresh breast sample will be flash-frozen for drug assay. 2) An aliquot of plasma from the research blood sample drawn with a 10 mL Lavender top tube (K2EDTA) at the Day of Surgery (study visit 1) will be to obtain plasma for measurement of circulating drug concentrations. Measurement of drug metabolites (tamoxifen, N-desmethyltamoxifen, E and Z isomers of both 4-OHT and endoxifen) (see the session 7.1, the schedule of event table footnote #9 for details). These fresh frozen tissue samples along with the paraffin block (Sample B in Figure 2), plasma, and buffy coat samples will be sent as a single shipment for each participant (frozen samples on dry ice) to NU from participating sites. FFPE blocks will be shipped in cold condition. At NU-PCF, the Sample B FFPE will be sectioned and stained with H&E to determine the tissue composition of the drug concentration sample. The histology findings from this research sample will not be reported back to clinical teams.

#### 10.2.2 Mastectomy sampling procedures (for subjects who opt for mastectomy)

At five sites (Cleveland Clinic, Mayo Clinic, Duke, St Elizabeth, University of Kansas), the drug concentration samples will be harvested by the grossing pathologist as described above in Section 10.2.1. The location of these two samples will be 1) superficial, one centimeter from the superficial surface of the mastectomy specimen, and 2) deep, one centimeter from the deep aspect of the mastectomy specimen. These samples may be taken from the location that is remote to the known location of the DCIS.

At two sites (NU and MSKCC) the mastectomy specimen will be grossed according to the scheme developed for a previous topical gel study, described above and depicted in Figure 2B.

#### 10.2.3 Paraffin blocks: As each subject is enrolled, the sites will indicate on the pre-enrollment form whether the DCNB was performed at the enrolling institution, or elsewhere. If elsewhere, the name of the

hospital and contact information for the Pathology Department of that hospital will be provided. If DCNB was not done at the enrolling institution, NU-PCF NU PCF will work with the enrolling site as needed to acquire DCNB material from the site where the DCNB was performed. If DCNB was done at the enrolling institution, the study coordinator will place a request for that block to be retrieved as soon as the surgical date is known, to avoid delays caused by block retrieval.

At the end of study participation, for each subject, the paraffin blocks of the DCNB (if done at the enrolling institution) and the surgical samples will be assembled by each site as soon as the final pathology on the surgical sample has been reported. The study consent will include a statement providing permission to the hospitals involved in diagnosis and therapy (which may not be the same) to release the DCNB block and a selected surgical block to NU for study purposes. At NU PCF, the pre- and post-therapy sample blocks will be sectioned at the same time following the completion of participation of each subject. A minimum of 15 sections will be taken for: H&E, Ki67, DCIS-Score and other markers (CD68, COX2, p16), cytokeratin (CK) as epithelial classifier and at least one extra for possible repeats. All sections will be saved, vacuum-sealed and cold, until the conclusion of the study. In this way, pre- and post-therapy sections for each biomarker will be processed in the same batch.

*Slide submission for Exact Sciences DCIS-Score:* Eight unstained slides of DCBN pre-therapy block will be submitted immediately to GHI (so that the data can be used for radiation therapy decision if needed). Eight unstained slides of post-therapy block will be reserved in the NU PCF and shipped as a single batch after the study is complete and all participant samples have been received at NU.

*Institutions that do not allow release of paraffin blocks despite participant consent.* These institutions will provide unstained sections of the paraffin block as detailed above.

*Institutions that do provide paraffin blocks:* these will be returned to the institution where the sample was taken once the protocol-defined sections have been taken, typically within 3 months of submission to NU.

#### *10.2.4 Timing of sample*

Specimen is obtained without regard to time of day or fasting, it will be determined by time of study visits. Circulating biomarkers are not significantly affected by time of day.

#### *10.2.5 Labeling of specimen*

Labeling will include protocol number and subject ID, 3-letter study site code, date and time of collection, type of sample and sample number as defined in protocol for breast tissue (see above Figure 2B)

#### *10.2.6 Tracking of specimens*

Each laboratory will email [contact] upon shipment of specimens to another site. Information provided will include PID, visit date, type of specimen, and number of specimens.

#### *10.2.7 Temperature storage requirements*

- FFPE samples will be stored and shipped cold
- Fresh tissue will be stored at -80 degrees C and shipped on dry ice
- Blood will be processed and aliquoted to yield serum, plasma, Buffy coat, stored at -80 degrees C and shipped on dry ice.

#### *10.2.8 Storage duration*

Samples will be stored until analysis are completed and published, at which point it will be transferred to the DCP repository.

### **10.3 Shipping Instructions**

### ***10.3.1 Shipping of samples to NU***

All samples on each participant will be sent in a two simultaneous shipments (one frozen shipping with dry ice, and one cold shipping) to NU following Visit 2. This will consist of i) drug assay samples (A and B in Figure 2A or 1-5 in Figure 2B); ii) pre- and post-intervention blood; iii) pre- and post-therapy paraffin blocks or sections of the paraffin block, from institutions that do not allow release of paraffin blocks. The study consent will specifically include permission for hospitals to release blocks to NU. Thus, as each subject completes participation, her samples will arrive at NU in a single batch, minimizing the chances of missing or misplaced samples.

### ***10.3.2 Shipping of samples from NU***

- Unstained paraffin sections from the baseline DCNB sample to Exact Sciences will be sent one at a time (90 shipments).
- Unstained paraffin sections from the post- therapy surgical sample to Exact Sciences will be batch-shipped at the end of the study.
- Plasma samples (lavender top tube) to the Northwestern University Comprehensive Metabolic Core Lab and plasma samples (blue top tube) to the Northwestern Memorial Hospital Hemostasis Lab and Quest Diagnostics will be batch-shipped at the end of the study
- Plasma (lavender top tube) and tissue samples to Hormone Laboratory of Haukeland University Hospital will be batch-shipped at the end of the study.

All samples will be shipped in compliance with the International Air Transport Association (IATA) Dangerous Goods Regulations.

## **10.4 Tissue Banking**

Biologic specimens collected during the conduct of each clinical trial that are not used during the course of the study will be considered deliverables under the contract and thus the property of the NCI. At study completion, NCI reserves the option to either retain or relinquish ownership of the unused biologic specimens. If NCI retains ownership of specimens, the Contractor shall collect, verify and transfer the requested biologic specimens from the site to a NCI-specified repository or laboratory at NCI's expense.

## **11. REPORTING ADVERSE EVENTS**

**DEFINITION:** AE means any untoward medical occurrence associated with the use of a drug in humans, whether or not considered drug related. An AE can therefore be any unfavorable and unintended sign, symptom, or disease temporally associated with participation in a study, whether or not related to that participation. This includes all deaths that occur while a participant is on a study.

Please note that all abnormal clinical laboratory values that are determined to be of clinical significance based on a physician's assessment are to be reported as AEs. Those labs determined to be of no clinical significance or of unknown clinical significance (per the physician's assessment) should not be reported as AEs. Any lab value of unknown clinical significance should continue to be investigated/followed-up further for a final determination, if possible.

A list of AEs that have occurred or might occur can be found in §6.2 Reported Adverse Events and Potential Risks, as well as the Investigator Brochure or package insert.

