### 3.8 *Handling of subjects who elect not to complete protocol-specified therapy.*

Every attempt will be made to retain all subjects for the entire duration of protocol-specified therapy. However, some participants may opt for early surgery. In this case, endpoints will be measured if more than 4 weeks of therapy have been completed (blood, tissue biomarkers and drug concentrations).

3.9 *Safety monitoring:* since oral tamoxifen is a widely used agent with a well-known safety/toxicity profile, we have been able to define exclusion criteria to avoid women for whom there will be safety concerns (e.g. those with a history of thromboembolism, and current smokers). Given the duration of intervention (maximum 10 weeks) it will not be necessary to use laboratory tests to monitor toxicity of oral tamoxifen other than the comprehensive chemistry panel at the pre- and post-treatment visits. The safety of the 4-OHT gel is also well established, since it is a metabolite of tamoxifen; the only unique toxicity to be expected would be skin irritation, which was observed for one participant in our previous trial, and has been reported to be infrequent in other, larger studies [39].

3.10 *Duration of study:* we anticipate that overall recruitment will cover months 1-24. The last subject should complete participation by month 27. Data assembly, cleaning, and biomarker evaluation will occur in months 24-36.

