### SCHEDULE OF EVENTS

Evaluation/ Procedure	Registration/ Screen 1	Randomization 	Study visit 1 (day of surgery) 	Study visit 2 (within 21 days after surgery)
Informed Consent	X			
Assess Eligibility	X			
Medical History	X		X 	
Physical Exam	X		X 	X
Vitals 	X		X	X
Breast Cup Size	X			
Blood draw for CBC and chemistry profile	X		X	
Research blood draw	X 		X 	
Pregnancy test 	X		X	
Menstrual period date 	X		X	X
BESS questionnaire 	X		X 	
Concomitant Medications	X		X 	
Dispense Study Agent		X		
Collect Study Agent			X 	
Review Agent Diary/Record		X	X 	
Adverse Events			X 	X
Fresh breast sample collection			X	
Record location & depth of lesion in breast			X	
Request paraffin blocks of core biopsy & surgery 		X (core biopsy)		X (surgical)
Assemble samples & mail to NU PCF				X
Phone calls timed from day 1 of intervention (up to 4 total) 		Weeks 1, 4  , 8 		0-5 weeks after Study Visit 2 

1. ECOG performance status, height, weight, blood pressure, pulse, and temperature
2. Research blood at Baseline (Screen 1) includes:
  - Two 2.7mL blue top tubes (Citrate) to obtain plasma for Coagulation panel assays.
  - Two 10 mL lavender top tubes (K2EDTA) to obtain plasma and buffy coat (WBCs for DNA/RNA isolation). Plasma will be obtained for 1) IGF-1, IGFBP-3, and SHBG assays; 2) steroid hormone assays (estradiol, progesterone). Buffy coat will be collected for future assessment of CYP2D6 polymorphisms in tamoxifen metabolism (refer section 10.2 for details).
3. Pregnancy tests will be performed on all women with child-bearing potential.
4. Record last and estimated next menstrual period at the Screen 1 visit. Confirm and record actual menstrual period date by a phone call to participant 1 week after the estimated date. Record last and estimated next menstrual period date at Visit 1. Confirm and record actual menstrual period date at Visit 2 or the final phone call.
5. Participants must be randomized within 90 days of DCNB and must start drug within 5 days after randomization.

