#### **CTCAE v4.0 general severity guidelines:**

Grade	Severity	Description
1	Mild	Mild; asymptomatic or mild symptoms; clinical or diagnostic observations only; intervention not indicated.
2	Moderate	Moderate; minimal, local or noninvasive intervention indicated; limiting age-appropriate instrumental activities of daily living (ADL)*.
3	Severe	Severe or medically significant but not immediately life-threatening; hospitalization or prolongation of hospitalization indicated; disabling; limiting self-care ADL**.
4	Life-threatening	Life-threatening consequences; urgent intervention indicated.

Grade	Severity	Description
5	Fatal	Death related to AE.

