### 11.1.5 Follow-up of AEs

All AEs, including lab abnormalities that in the opinion of the investigator are clinically significant, will be followed according to good medical practices and documented as such.

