
**Adverse Events.** AEs will be assessed using CTCAE. Worst grade toxicity for each AE type will be summarized by arm using descriptive statistics. For each AE type, proportions of patients experiencing toxicity of any grade will be compared between arms using Fisher's exact test.

**Treatment Compliance.** Compliance will be defined as described in Section 5.7. Each patient will be determined as compliant or non-compliant for each treatment component (capsules compliance and gel compliance). Treatment compliance rates based on active ingredient component will be summarized using proportions, and compliance rates will be compared between arms using Fisher's exact test. In addition, in order to determine whether compliance is different for capsule vs. gel administration, within-subject differences in treatment component compliance will be analyzed using the McNemar test among all patients, regardless of treatment arm.

**Subgroup analysis.** Exploratory analyses will be conducted by menopausal status (pre or peri-menopausal vs. post-menopausal). Descriptive statistics will be used to summarize study endpoints by group. In addition, linear regression models as described above will be used with the addition of menopausal status and possibly its interaction with treatment as predictors. Model-based linear contrasts will be constructed to test relevant treatment noninferiority or superiority hypotheses within subgroups. Similar analyses will be conducted in the subgroup of women with invasion in the post-treatment surgical sample.

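### CBC and chemistry results enter the safety analysis only as adverse events a physician judges clinically significant; the values are never compared by arm, so modest differences would probably be missed.

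*Combined protocol and SAP*

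**What the plan says.** Section 3.9 (Safety monitoring) holds that tamoxifen needs no laboratory toxicity monitoring "other than the comprehensive chemistry panel at the pre- and post-treatment visits". In the Schedule of Events, the row "Blood draw for CBC and chemistry profile" is marked at Screen 1 and Study Visit 1 (day of surgery) only. Study Visit 2 has no laboratory test. Section 7.2.3 holds randomization until the baseline results are reported, so every randomized woman should have a baseline. Section 3.4 ends dosing on the day before surgery.

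Section 11 says that "all abnormal clinical laboratory values that are determined to be of clinical significance based on a physician's assessment are to be reported as AEs". It keeps off the form "Those labs determined to be of no clinical significance or of unknown clinical significance", while asking that values of unknown significance be pursued to a final determination where possible. Section 11.1.5 uses the same test for follow-up: "All AEs, including lab abnormalities that in the opinion of the investigator are clinically significant".

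The general severity table in 11.1.3 includes in Grade 1 "clinical or diagnostic observations only; intervention not indicated". Section 13.5.4 summarizes the worst grade of each AE type by arm, and "proportions of patients experiencing toxicity of any grade will be compared between arms" with Fisher's exact test. Nothing in section 13 provides for a change from baseline, a shift table or value-based grading of the CBC/chemistry panel.

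Other laboratory measures are handled differently. Section 2.3.3 names the coagulation proteins and IGF-1, IGFBP-3 and SHBG as toxicity-related secondary endpoints, and 13.5.4 compares them between arms as continuous values.

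**The concern.** Section 13.1 justifies the comparison partly on the gel being less toxic. The plan collects a paired safety panel but gives its numbers no analysis. Each result is reduced to a yes/no judgement by a physician at one of seven sites, and only the yes answers are counted.

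Three features add to the loss:

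- **Asymptomatic abnormalities.** A value out of range without symptoms or need for intervention fits the protocol's Grade 1 description, and is also the kind a physician may well call not significant. The any-grade comparison then omits it.
- **A second judgement.** The only post-baseline panel falls on the day of surgery. From that day, 11.1.1.2 has AEs recorded only if they are not related to surgery.
- **An unused baseline.** Section 4.1.4 admits women with bilirubin, AST/ALT or creatinine up to 1.5 times the upper limit of normal. An abnormal Visit 1 value may therefore have been present at entry, and no planned analysis sets the two results side by side.

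At stake is how a sparse laboratory AE table is read. It could pass for evidence of no difference when the values were never compared.

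**Working it through.** **The plan's own figure.** The documents give no power, rate or SD for laboratory toxicity. As a check on method, the noncentral t calculation used below was applied to the primary endpoint in 13.4.2: n = 40 per arm, SD 5.4, margin 2.6, one-sided 0.10. It gives 80.52%, against 80.5% stated.

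**Inputs from the documents.** Allocation is 1:1. At most 100 women start intervention, so up to 50 per arm (13.4.2). Section 3.2 expects 45 per arm to be evaluated for study endpoints. Both sizes are used.

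**Assumptions.** Two-sided alpha is 0.05 (not stated for AEs). The true shift in one arm is 0.5 SD on the (log) value. The pre-post correlation ρ is 0.3, 0.5 or 0.7. In the unshifted arm, the share p of values extreme enough to be called clinically significant is 2%, 5% or 10%.

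**Route 1: AE form and Fisher's test.** The shifted arm's rate is 1 − Φ(Φ⁻¹(1 − p) − 0.5). For p = 5% this is 1 − Φ(1.645 − 0.5) = 12.6%. Power is by exact enumeration, first with every such value reported.

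| Rates compared | Power, 45 per arm | Power, 50 per arm |
|---|---|---|
| 2% vs 6.0% | 2% | 3% |
| 5% vs 12.6% | 13% | 14% |
| 10% vs 21.7% | 24% | 26% |

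With no events in one arm, significance needs 6 in the other (6 vs 0 at 50 per arm, p = 0.027). If only half of the values in the 5% row are reported, power at 50 per arm falls from 14% to 3%.

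**Route 2: ANCOVA on the values.** In SD units, SE = √[(2/n)(1 − ρ²)]. At n = 45 and ρ = 0.5, SE = √(0.0444 × 0.75) = 0.183, the noncentrality is 0.5/0.183 = 2.74, and power is 77%.

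| ρ | Power, 45 per arm | Power, 50 per arm |
|---|---|---|
| 0.3 | 69% | 74% |
| 0.5 | 77% | 82% |
| 0.7 | 91% | 93% |

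**Larger differences by the AE route** (50 per arm, Fisher's test, by share of abnormal values reported):

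| True rates | All reported | Half | A quarter |
|---|---|---|---|
| 20% vs 5% | 51% | 16% | 2% |
| 30% vs 5% | 90% | 45% | 10% |
| 50% vs 10% | 99% | 75% | 30% |

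**A smaller shift.** At 0.3 SD and 50 per arm, analysis of values gives 32% power by t-test and 40% by ANCOVA at ρ = 0.5. With 5% of the unshifted arm beyond the cut-off and all reported, the AE route gives 4%.

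**The case against.** The strongest objection is that the protocol already measures the toxicity that matters to its case. Sections 2.1 and 6.2 emphasize thromboembolism, endometrial cancer, hot flashes and vaginal symptoms, not liver enzymes, creatinine or blood counts. Coagulation proteins, estrogenic markers and the BESS questionnaire address much of that and are analysed without a physician filter. Section 3.9 also gives reasons for limited laboratory monitoring: a well-known agent and at most 10 weeks of exposure. This stands. It confines the point to the CBC/chemistry panel, and a reader who inferred that all laboratory toxicity is filtered would be wrong. It does not explain why a panel drawn before and after treatment for safety goes unanalysed.

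A reader might also infer that the reporting rule removes Grade 1 laboratory events outright. It does not: the filter is significance, not grade, and a Grade 1 value judged significant is reported. Nor are values of unknown significance certain to stay out. Unscheduled follow-up is allowed and AE recording runs through Visit 2, although no scheduled test would settle them.

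Finally, the two power figures answer different questions. A 0.5 SD mean shift may lie wholly within normal limits, and Fisher's test is weak for any uncommon AE at this sample size. Both are fair. They are reasons to present the added analysis as description with confidence intervals. They do not justify leaving the values out.

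The case report forms and the Data and Safety Monitoring Plan are not part of these documents, so whether the values are captured or reviewed elsewhere cannot be checked.

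**Conclusion.** The point holds for the CBC/chemistry panel. Its any-grade comparison is incomplete, and a modest arm difference would probably be missed. Under the assumptions shown, power is about 2 to 26% by the AE route against 69 to 93% by ANCOVA on the values. The shift, correlation, cut-offs, reporting share and alpha are all assumed, because the documents supply none of them.

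Two stronger conclusions are tempting but unsupported. One is that any real difference would almost surely be missed: a large difference with most abnormal values reported could be found, and no document fixes the size or the reporting share. The other is that the rule favours the gel: the trial is double-blind with matching placebos, so the filter should mainly cost sensitivity. The primary result and the named toxicity endpoints are unaffected. The change is worth making because it is cheap and uses data already drawn.

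**What to change.** Leave the AE reporting rule in section 11 as it is. Add to 13.5.4, for leukocytes, platelets, bilirubin, AST, ALT and creatinine (the eligibility analytes in 4.1.4):

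1. Shift tables from baseline to Study Visit 1 by arm, with the CTCAE v4.0 grade derived from the numeric result whatever the physician's judgement.
2. The between-arm difference at Study Visit 1 with a 95% confidence interval, from the ANCOVA already specified (baseline value and menopausal status as covariates; log scale if skewed).

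Label both as descriptive safety analyses without multiplicity adjustment.

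The cost is some SAP text, a few tables, and entry of the values on the case report form if they are not already captured. No extra blood draw is needed. The drawbacks are six more unadjusted comparisons and a post-baseline panel that needs cautious reading, because it is drawn on the day of surgery, after the last dose. The added analysis would still have limited power for shifts as small as 0.3 SD.
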